Appendix 4. List of Drugs Known to Predispose to Torsades de Pointes

The medications which are known to be associated with a risk of TdP and known to prolong the QTc interval are listed in the CredibleMeds® TdP risk category (<https://www.crediblemeds.org>).

(CredibleMeds® is associated with University of Arizona Cancer Center for Education and Research on Therapeutics [CERT]: “Torsades List: Drugs with a Risk of Torsades de Pointes,” Advisory Board).

**Appendix 5. Definition of Refractory and Relapsed AML (ELN 2017
Recommendation)⁵**

Refractory Disease:

- No complete remission (CR) or CR with incomplete hematologic recovery (CRi) after 2 courses of intensive induction treatment; excluding patients with death in aplasia or death due to indeterminate cause.

Relapsed Disease:

- After CR without minimal residual disease (CR_{MDR-}), CR, or CRi, bone marrow blasts $\geq 5\%$; or reappearance of blasts in the blood; or development of extramedullary disease.

## 1. VERSION HISTORY

This Statistical Analysis Plan (SAP) for study B1761031 is based on the protocol dated 27Jun2018. The SAP was amended to clarify some analyses, to update based on changes in standards, to address COVID-19, and to document reporting strategy for reporting summaries of adult patients separately from pediatric patients.

**Table 1. Summary of Major Changes in SAP Amendments**

SAP Version	Version Date	Change	Rationale
1	27 June 2018	Not Applicable	Not Applicable
2	21 April 2021	PK: “total calicheamicin” was corrected to “unconjugated calicheamicin”	Correction was made throughout the SAP in alignment with the protocol.
		AUC 0-72 , AUC 0-336 were added to PK parameters.	These parameters are estimable with the collected data.
		Definition of positive ADA & NAb was clarified.	The titer values and classification of positive were clarified based on the analytical reports.
		CR and CRi: the units for the platelet count requirement were corrected.	A PACL corrected the unit to 100x10  /L (100,000/µL).
		CCI [REDACTED]	CCI [REDACTED]
		Clarified that Myelosuppression is also an AESI.	Myelosuppression is an AESI that had been omitted from SAP version 1.
		Reporting of laboratory parameters, particularly for urinalysis results, were clarified.	Additional clarification and details for reporting were provided to facilitate organization of summaries as CTC graded or not.
		Analysis sets (PK parameter [REDACTED] details were updated. Immunogenicity analysis set was added.	PK parameter analysis set was generalized to be consistent with other parts of the SAP. CCI [REDACTED] Immunogenicity analysis set was added for consistency with standards.
		CCI [REDACTED]	CCI [REDACTED]
		Details were added to describe that results for adult patients to	Separate CSRs are planned due to the estimated time to complete the pediatric enrollment.

SAP Version	Version Date	Change	Rationale
		reported separately from pediatric patients.	
		The last cycle definition was updated to the min (last dose +36, start of subsequent anticancer therapy)	The change is consistent with the safety reporting period, and standard definitions that consider start of subsequent anticancer therapy.
		Additional categorizations ECG parameters were added to summaries. Clarification was added whether triplicate averages or individual replicates are included in summaries.	Given the focus on ECGs, the additional categorizations were felt to be relevant. The clarifications about replicates was based on standards.
		Derivation of QTcS: The estimated slope was clarified to be based on individual replicates and changed to be based on only the individual replicates selected as baseline.	It was felt to be most relevant to derive QTcS based on only the individual replicates selected as baseline.
		Statistical details for LS means, SE, and CI were provided and was updated to include only data from Cycle 1.	Further details for the linear model were provided for clarity. Only data from Cycle 1 will be included because Cycle 2 was optional and at the investigator's discretion.
		Analyses for impact of COVID-19 pandemic were added.	Since study enrollment and conduct was ongoing during the COVID-19 pandemic, conventions and analyses were added per company guidance
		Missing PK data conventions were clarified.	The clarifications were made consistent with standards.
		References to listings were modified.	Consistent with standards changes, the focus is on listings required for an ICH CSR.
		Plots of PK parameters were removed.	The plots were to contain summaries for adult and pediatric patients, but pediatric enrollment has not completed
		Descriptive statistics summary of PK concentrations were added. Mean plots were removed.	The descriptive summary was inadvertently omitted from SAP version 1. Consistent with current reporting guidance some outputs were omitted to streamline reporting.
		Graphical summary of change in QTcF from baseline was added.	A graphical summary for the primary endpoint was added to streamline the presentation in the CSR.
		The descriptions of the immunogenicity summaries were modified.	Updates are consistent with current standard summaries.

SAP Version	Version Date	Change	Rationale
		Overall Survival: the probability of an event at 6 months was added. [REDACTED]	The probability of an event at 6 months was added to provide an estimate in the event the 12 month probability is zero. [REDACTED]
		Summaries of height, weight, and BMI were removed from Baseline Characteristics.	The summaries were removed to facilitate production of in-text CSR tables consistent recently introduced conventions for studies.
		Prior and Follow-Up HSCT definition has been clarified.	The definition was inadvertently not previously provided.
		Summary of protocol deviations was added.	This addition is consistent with the standard process.
		Clarifications of summaries including categorization of transplant relative to GO dose which had a typographical error, and the start of Cycle 2 which needed an additional category were added.	The updates were made to correct typographical errors, and details were added consistent with the CRF.
		The high level summary of AEs was updated, and summary tables of AE that had actions taken due to the AE were added. Additional summaries were added for in-text tables.	The update is consistent with current standard tables and oncology reporting conventions. Updates to AE summaries were made to facilitate production of in-text CSR tables consistent with recently updated oncology conventions.
		A summary of AESI of INFUSION RELATED REACTIONS by ADA status was added.	The summary was added to assess the impact of ADA on safety.
		Laboratory summaries were changed from worst (maximum) grade to shift from baseline tables; similarly non-CTC graded laboratory summaries were changed to shift, and summary of liver function tests was added.	Updates to summaries were made to facilitate production of in-text CSR tables and consistent with recently updated oncology conventions.
		ECG maximum increase from baseline as a continuous variable summarized with descriptive statistics was removed.	It was considered sufficient to summarize this categorically.

## 2. INTRODUCTION

This SAP provides the detailed methodology for summary and statistical analyses of the data collected in study B1761031 titled: A single arm, open-label, Phase 4 study evaluating QT interval, pharmacokinetics, and safety of gemtuzumab ozogamicin (GO; MYLOTARGTM) as a single-agent regimen in patients with relapsed or refractory CD33-positive acute myeloid leukemia (AML). This document may modify the plans outlined in the protocol; however, any major modifications of the primary endpoint definition or its analysis will also be reflected in a protocol amendment. Any deviations from this analysis plan will be described in the Clinical Study Report.

### 2.1. Study Objectives

**Primary Objective:** To assess the effect of GO on the QTc interval

**Secondary Objectives:**

- To characterize the PK of single-agent GO following the fractionated regimen (i.e., 3 mg/m^2 on Days 1, 4, and 7)
- To assess the safety of GO with fractionated dosing of 3 mg/m^2
- To assess the immunogenicity of GO
- To assess response and overall survival

CCI

### 2.2. Study Design

This is a single-arm, open-label, Phase 4 study evaluating the effect of gemtuzumab ozogamicin (GO) on the QTc, pharmacokinetics, safety, and immunogenicity of GO as a single-agent monotherapy in adult and pediatric patients with relapsed or refractory CD33-positive AML. Approximately 50 adult (age  $\geq 18$  years) patients and 6 pediatric ( $12 \leq \text{age} \leq 17$  years) patients will be enrolled.

**Treatment Plan:** Three doses of GO 3 mg/m^2 (up to one vial) as a 2-hour intravenous infusion on Days 1, 4, and 7 at each cycle, up to 2 cycles. A second cycle of GO will be allowed at the investigator's discretion for patients who meet the following criteria after Cycle 1: Bone marrow with a decrease of blast percentage to at least 25% or a decrease of pretreatment blast percentage by at least 50%; **and** blood count with neutrophils  $\geq 1,000/\mu\text{L}$

and platelets  $\geq 50,000/\mu\text{L}$ , except in patients where the bone marrow blasts  $\geq 5\%$  and the decrease in neutrophils and platelets is thought to be due to the underlying leukemia.

After GO treatment, subsequent anticancer therapy such as consolidation or conditioning regimen and/or HSCT could be considered at the investigator's discretion. A minimum interval of 2 months is recommended between the last dose of GO and HSCT.

**Summary of Assessments:** Triplicate ECGs will be performed at screening, baseline (prior to dose on Day 1) and immediately preceding serial PK draws. All triplicate ECG tracings will be sent to an independent ECG core laboratory for blinded manual interval measurements.

Blood samples will be collected from all participating patients for PK analysis according to the PK schedule. Samples will be collected prior to each dose and at time points around the maximum concentration ( $C_{\max}$ ), i.e. at the end of the 2-hour infusion, in order to characterize the QTc-concentration relationship.

Anti-drug antibody (ADA) samples will be collected as specified in the protocol. Samples will be analyzed for ADAs using a tiered approach of screening, confirmation, and titer determination. Samples that test positive for ADA will be further characterized to determine whether neutralizing antibodies (NAb) are present.

CC1

The active safety monitoring duration will be up to 36 days after the last dose of GO or starting of subsequent anticancer therapy, including consolidation and/or conditioning regimens, whichever occurs first. Any events of veno-occlusive disease (VOD) and sinusoidal obstruction syndrome (SOS) will be reported as serious adverse event (SAE) during the study duration. Details of the HSCT will be collected in order to assess the impact of the fractionated regimen of GO on the risk of VOD/SOS with previous or subsequent HSCT.

After receiving the study treatment, blood cell and differential counts will be examined 3 times a week after GO dosing until having determination of remission status; subsequently CBC and differential counts will be collected once weekly until 36 days after the last dose of GO or until start of subsequent anticancer therapy, e.g., consolidation or conditioning regimen.

Efficacy evaluation and determination of remission status by blood and bone marrow aspiration (and biopsy if applicable) will be conducted at the end of each cycle after recovery of blood counts is observed or at a maximum of 36 days after the last dose of GO treatment (EOT) using European Leukemia Net (ELN 2017) recommendations.

Study duration for each patient is a total of 12 months from enrollment, survival data will be collected for the study duration of 12 months.

### **3. ENDPOINTS AND BASELINE VARIABLES: DEFINITIONS AND CONVENTIONS**

#### **3.1. Primary Endpoint**

##### **3.1.1. QTc interval**

Change from baseline in corrected QT interval (QTc) using Fridericia's heart rate correction. Refer to Section 5.2.8 for details of derivations.

#### **3.2. Secondary Endpoints**

##### **3.2.1. PK parameters**

The following PK parameters will be calculated for GO (represented by total hP67.6 antibody, conjugated calicheamicin, and unconjugated calicheamicin) from the concentration-time values using standard noncompartmental methods:  $AUC_{last}$ ,  $AUC_{0-72}$ ,  $AUC_{0-336}$ ,  $C_{max}$ ,  $T_{max}$ , and if data permits  $AUC_{inf}$ ,  $t_{1/2}$ ,  $CL$ ,  $V_{ss}$ . A tabular summary of these noncompartmental PK parameters and analyses is presented in Table 3.

##### **3.2.2. Immunogenicity**

Samples for ADA will be analyzed using a tiered approach of screening, confirmation, and titer determination. Samples that test positive for ADA to GO will be further tested for specificity (in presence of purified hP67.6 naked antibody and in the presence of calicheamicin payload) and characterized to determine whether NAb are present or absent.

ADA will be classified as negative if the titer value is less than the minimum required dilution, i.e., titer <75, and positive otherwise (titer 75 or greater).

NAb will be classified as negative if the titer value is less than the minimum required dilution, i.e., titer <20, and positive otherwise (titer 20 or greater).

##### **3.2.3. Best Response**

Efficacy evaluation and determination of remission status by blood and bone marrow aspiration (and biopsy if applicable) per the investigator will be classified according to European Leukemia Net (ELN 2017) recommendations according to the following categories. Thus the bone marrow will be assessed by the investigator after each cycle when blood count recovery (neutrophils  $\geq 500/\mu L$  and platelet  $\geq 50,000/\mu L$ ) is observed or at a maximum of 36 days after the last dose of GO regimen. The date of response is also dependent on the observation of the peripheral blood recovery mentioned in the criteria below. If Cycle 2 is to be administered, note that the Cycle 1 assessment is required to be conducted prior to the start of Cycle 2.

Response will be defined as CR or CRi which are defined as follows per ELN 2017:

- Complete Remission (CR): Bone marrow blasts < 5%; absence of circulating blasts and blasts with Auer rods; absence of extramedullary disease; ANC  $\geq 1 \times 10^9/L$  (1000/ $\mu$ L); platelet count  $\geq 100 \times 10^9/L$  (100,000/ $\mu$ L)
- CR with incomplete hematologic recovery (CRi): All CR criteria except for residual neutropenia; ANC  $< 1 \times 10^9/L$  (1000/ $\mu$ L); or thrombocytopenia; platelet count  $< 100 \times 10^9/L$  (100,000/ $\mu$ L)

Best response will be derived from the CRF values for the two cycles: as CR if either Cycle 1 or Cycle 2 are CR, or if no CR then if either Cycle 1 or Cycle 2 are CRi the best response is CRi. Patients without a documented CR or CRi will be considered as non-responders.

### 3.2.4. Overall Survival

Overall survival is defined as the time from start date to the date of death due to any cause. Patients last known to be alive as censored at the date of last contact.

Refer to Section 5.2.6 for derivation of the last contact date.

The start date for a patient is date of first treatment (if treatment start date is not available, then date of enrollment will be used)

CCI

### 3.4. Baseline Variables

ECG parameters: The last available planned triplicate measurements prior to first dose according to the date (selected from nominal time points of Screening and Cycle 1 Day 1 at 0 hours) will be used as baseline. Triplicate ECGs are collected; therefore the baseline for each ECG measurement is the average of the pre-dose measurements on the selected baseline day. Refer to Section 5.2.8 for further details of derivations concerning ECG parameters.

For safety (including Eastern Cooperative Oncology Group (ECOG) performance status, safety laboratory results, blasts in the bone marrow, blasts in the peripheral blood, immunogenicity) the last assessment performed on or prior to date of the first dose of study treatment will be designated as the baseline assessment. If there are no observations meeting these criteria, then baseline is considered missing. For laboratory data, if there are multiple assessments that meet the baseline definition on the same day without the ability to determine which was truly last, then the worst CTC grade will be considered as the baseline grade.

CD33 expression: CCI (percent positivity CCI [REDACTED] the baseline value will be based on the bone marrow sample that is the last available assessment on or prior to the date of first dose of study treatment. If there is no result available from bone marrow, then a result from a blood sample meeting the same criteria will be used. CCI [REDACTED]

Additionally, percent positivity will be categorized as < 30, 30 - <70,  $\geq$  70; CCI [REDACTED]

The date of first dose (start date) of study treatment is the earliest date of GO dosing.

The date of last dose of study treatment is the latest date of GO dosing.

No windowing will be applied when defining baseline. Although the protocol requires screening assessments to be performed within 28 days prior to first dose; values outside this window will not be excluded when determining baseline assessments.

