Abbreviations: aPTT = activated partial thromboplastin time; BM = bone marrow; C = Cycle; CAT = computed axial tomography; CBC = complete blood counts; D = Day; ECG = electrocardiogram; ECOG PS = Eastern Cooperative Oncology Group performance status; EOT = end of treatment; GO = gemtuzumab ozogamicin; HIV = human immunodeficiency virus; MRI = magnetic resonance imaging; PE = physical examination; PT = prothrombin time

1. All assessments should be performed prior to dosing with GO on the visit day unless otherwise indicated. Acceptable time windows for performing each assessment are described in the column headers. The exact enrollment day (Day 1) is the day when patient identifier is assigned with the first GO dose. The EOT is defined as 36 days after the last dose of GO or start of subsequent anticancer therapy, eg, consolidation and/or conditioning regimens.
2. The second cycle will be allowed at the investigator's discretion for patients who meet the following criteria after Cycle 1 (see also [Table 3](#) describing hematologic toxicities): Bone marrow with a decrease of blast percentage to at least 25% or a decrease of pretreatment blast percentage by at least 50%; **and** Blood count with neutrophils $\geq 1,000/\mu\text{L}$ and platelets $\geq 50,000/\mu\text{L}$, except in patients with the bone marrow blasts $\geq 5\%$, the decrease in neutrophils and platelets thought to be due to the underlying leukemia. Patients who do not meet these response criteria after the first cycle of GO will not be allowed to receive a 2nd cycle (see [Section 7.5](#)). Cycle 2 Day 1 must be started no later than 42 days after the last dose of GO (ie, Cycle 1 Day 7).
3. Informed Consent and assent for those patients under age 18 (or as specified per local policy/laws). Must be obtained prior to undergoing any study procedure.
4. CD33 immunophenotyping performed at screening on bone marrow (BM) or of circulating blasts in peripheral blood specimen by local laboratories. Surface CD33 expression should be measured by flow cytometry (flow-activated cell sorting, FACS); immunohistochemistry (IHC) analysis is allowed in patients with (1) dry tap; or (2) if BM specimen is inadequate and/or with insufficient circulating blasts for FACS. [CCI](#) [REDACTED]

C
C
I

5. [REDACTED]

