6. ECGs will be in triplicate (3 consecutive ECGs approximately 2 minutes apart). All ECGs will be sent to an ECG core laboratory vendor. ECG at screening will be used to determine patient eligibility. Ideally, the patient will be supine or reclined in a semi recumbent position for the entire infusion and for both pre- and post- infusion ECGs. To minimize artifact, the patient should not change position between the pre- and post-infusion ECGs. Additional ECGs may be done if clinically required. See [Table 2](#) for additional collection time points.
7. Pharmacokinetic samples: See [Table 2](#) for additional time points.
8. Medical History: To be collected within 28 days prior to first dose. Includes date of initial diagnosis with FAB subtype, prior AML therapies including HSCT and outcomes, and cytogenetics. Also, review study eligibility.
9. ECOG PS: Assessment is not required on Day 1 if acceptable screening assessment is done within 7 days prior to the start of investigational drug.
10. Patients with suspected extramedullary disease will have imaging assessment (eg, CAT or MRI) of all known disease sites.
11. Days 1, 4, and 7 laboratory samples should be collected prior to dosing.
12. Three times a week after GO dosing until determination of remission status (see [Section 7.5](#)); subsequently CBC and differential counts will be collected once weekly until EOT (or until start of Cycle 2 (if administered) or start of subsequent anticancer therapy).
13. Pregnancy test: Required in less than 7 days prior to Day 1.
14. Evaluations of HIV and hepatitis B serological tests and hepatitis C tests (see [Section 6.1](#)).
15. Efficacy evaluation and determination of remission status by blood and bone marrow aspiration (and biopsy if applicable) after recovery of blood counts is observed and/or at a maximum of 36 days after the last dose of GO treatment.
16. Adverse Event (AE) Assessments: Adverse events should be documented and recorded at each visit using NCI CTCAE version 4.03 up to 36 days after the last dose of GO or start of subsequent anticancer therapy, (eg, consolidation or conditioning regimen), whichever occurs first. Patients must be followed for AEs according to [Section 8](#). Sites should report related SAEs including VOD/SOS as warranted. Any occurrence of VOD/SOS is to be reported as SAE to Pfizer Safety and recorded in the case report form (CRF see [Section 7.4.1](#)).

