6.2.2.1. Cycle 1 Day 1 (GO Treatment)

[figure not shown]
- On Day 1 patients may be admitted at the site for 24 hours for pharmacokinetic/pharmacodynamic (PK/PD) sampling at investigator's discretion. Hospitalization beyond Day 1 is per standard of practice and investigator judgment. If there is prolongation of hospitalization, consider if SAE criteria are met (see [Section 8.2.4](#)).
- Laboratory specimen will be collected per the [Schedule of Activities](#) (and assessed per [Section 7](#)). Results of complete blood counts, and serum chemistry tests must be checked before dosing. Patients will have a blood sample collected prior to GO administration for the measurement of immunogenicity (antibodies to GO [ADA] and neutralizing antibody [NAb]).

C
C
I

- Patients will be weighed for body surface area (BSA) calculation.
- Physical examination (PE) performed with clinical judgment evaluating potential areas of AML relapse and any clinically significant abnormalities which may include the following body systems: general appearance, skin, head/eyes/ears/nose/throat, heart, lungs, testes, abdomen, extremities, neurological, back/spinal, and lymph nodes; including worsening of medical history conditions.
- Vital signs including blood pressure, pulse, and body temperature will be performed prior to GO infusion and 2 hours after the infusion is complete (see [Table 1](#)). ECOG PS assessment will be conducted if acceptable screening assessment is not done within 7 days prior to the start of investigational drug.
- Pre-medication should be given before GO infusion. See [Section 5.4.1](#) and [Section 5.4.2](#) for administration of premedication and GO, respectively.
- Electrocardiograms (ECGs) will be collected in all patients according to [Schedule of Activities \(Table 2\)](#) and as described in [Section 7.1](#). The ECGs will be collected in triplicate (3 consecutive ECGs approximately 2 minutes apart). Predose ECGs will be performed prior to GO dosing, after administration of premedications. Triplicate ECGs will also be performed prior to selected serial PK draws, around the time when the C_{max} is expected and immediately before the end of the infusion, ie, prior to the Hour 2 PK sample collection (within 15 minutes).³

C
C
I

- Pharmacokinetic (all patients) 

[figure not shown]
PK collections will include predose (Hour 0),
Hour 1, 2, 4, 6, and 24 as described in [Schedule of Activities \(Table 2\)](#).  Adverse events

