7.4. Safety Assessments

Safety assessments include adverse events (AEs) graded according to the National Cancer Institute Common Terminology Criteria for Adverse Events (NCI CTCAE, version 4.03), clinical examination (including blood pressure and pulse), ECGs, and laboratory tests (hematology, chemistry, coagulation and urinalysis).

Additional (unscheduled) assessments should be conducted if laboratory values are abnormal (or if clinically indicated) and repeated until resolution, until return to baseline, or until NCI CTCAE Grade ≤1.

Safety assessments will be conducted until patient discontinues from the study or as protocol specified for 36 days after the last dose of GO or start of subsequent anticancer therapy such as consolidation and/or conditioning regimen ([Schedule of Activities Table 1](#)). Survival status will be collected for the study duration of 12 months for each patient.

The laboratory tests specified in [Appendix 3](#) will be conducted.

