Several laboratory tests have bi-directional grading criteria defined so that both low (hypo) and high (hyper) values will be graded separately. Each criterion will be summarized separately. In the cases where a value is graded as a Grade 1, 2, 3, or 4 for one of the directions, that value will also be assigned as a Grade 0 for the opposite direction for that test. For example, a value meeting the criteria for Grade 3 Hypercalcemia will be classified as a Grade 0 Hypocalcemia.

The following summaries will be provided for the safety analysis set.

The denominator for percentages will be the number of patients treated in the group being summarized with at least 1 post baseline assessment of the laboratory parameter.

Displays will be organized by laboratory category: Hematology parameters including coagulation parameters will be summarized together, chemistry parameters will be summarized together, and urinalysis parameters will be summarized together. Laboratory parameters with CTCAE grades will be summarized separately from laboratory parameters with no CTCAE grades.

For each CTCAE term, patients will be counted according to the worst (maximum) CTCAE grade on treatment (excluding baseline values). Baseline is defined in Section 3.4. If there are multiple assessments that meet the baseline definition on the same day without the ability

to determine which was truly last, then the worst CTC grade will be assigned as the baseline CTC grade.

The following summary tables will be created:

- Shift summary of laboratory parameters of baseline CTCAE grade by maximum post baseline CTCAE grade.
- Shift summary of laboratory parameters from  $\leq$  Grade 2 at baseline to  $\geq$  Grade 3 post-baseline.

The non-CTC graded laboratory tests (red blood cells, hematocrit, BUN, LDH) along with urinalysis test (pH) will be presented according to the following categories overall: below normal limit, within normal limits, and above normal limits. In the unlikely event that for a given participant, clinically significant abnormalities are noted in both directions (eg,  $>$  ULN and  $<$  LLN), then both abnormalities are counted. The remaining urinalysis tests (albumin, glucose, blood/hemoglobin, ketones/acetone) will be categorized as negative or positive.

A shift summary of laboratory test results with no CTCAE criteria of baseline assessment by worst on-treatment assessment will be created. .

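### The date-only baseline rule for safety laboratory tests can let an off-schedule sample drawn after the first infusion on Day 1 serve as the baseline

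*SAP*

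**What the plan says.** SAP Section 3.4 (Baseline Variables) sets one baseline rule for safety data, including laboratory results: "the last assessment performed on or prior to date of the first dose of study treatment will be designated as the baseline assessment". For laboratory data it adds a tie rule. It applies "if there are multiple assessments that meet the baseline definition on the same day without the ability to determine which was truly last", and "then the worst CTC grade will be considered as the baseline grade".

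SAP Section 6.6.3 (Laboratory Data) builds the shift tables from this baseline. For each CTCAE term, "patients will be counted according to the worst (maximum) CTCAE grade on treatment (excluding baseline values"). Two tables follow: baseline grade by maximum post-baseline grade, and shifts from Grade 2 or lower to Grade 3 or higher.

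SAP Section 3.5 starts the on-treatment period at the first dose of study treatment. Section 3.5.1 counts adverse events dated on the day of first dose as on-treatment.

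The protocol governs when samples are drawn. Table 1 footnote 1: "All assessments should be performed prior to dosing with GO on the visit day unless otherwise indicated". Footnote 11: "Days 1, 4, and 7 laboratory samples should be collected prior to dosing". Section 6.2.2.1, for Cycle 1 Day 1: "Results of complete blood counts, and serum chemistry tests must be checked before dosing". Section 7.4 also provides for extra tests: "Additional (unscheduled) assessments should be conducted if laboratory values are abnormal", or where clinically indicated.

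**The concern.** A baseline should describe the patient before exposure. The laboratory rule secures this only through the sampling schedule, because its own wording refers to the date of first dose and not to the start of the infusion. A same-day sample taken after the infusion satisfies it.

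If such a sample is chosen, a change after the first dose is recorded as the starting state. It is then removed from the on-treatment maximum, and the patient may sit in the wrong cell of the shift tables. Section 6.6.3 also notes that creatinine is graded partly against baseline, so a displaced baseline could alter later creatinine grades. The SAP would be treating one value as baseline under Section 3.4 although it falls in the on-treatment period of Section 3.5. An adverse event recorded for the same finding would be treatment-emergent.

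**Working it through.** The plan gives no figure on this point. The check follows the rules through the sampling schedule.

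**Step 1: scheduled samples.** Protocol Table 1 has one collection each of blood counts, chemistry and coagulation on Cycle 1 Day 1. Footnotes 1 and 11 place it before dosing, and Section 6.2.2.1 supports this for counts and chemistry. The next scheduled collection is Day 4. Scheduled post-infusion safety laboratory samples on Day 1: 0. For a patient with only scheduled samples drawn on time, the date rule picks the pre-dose value and there is no error.

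**Step 2: off-schedule samples.** Two routes remain: an unscheduled test under Protocol Section 7.4, or a scheduled sample drawn late. Either carries the date of first dose and so meets the definition in SAP Section 3.4.

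**Step 3: trace the grades.** The grades below are illustrative. Each pair is baseline grade, then worst post-baseline grade.

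| Case | Pre-dose | Day 1 after infusion | Worst from Day 4 | SAP rule | Pre-infusion baseline | Table of Grade ≤2 to ≥3 |
|---|---|---|---|---|---|---|
| A, order known | 1 | 3 | 2 | 3, 2 | 1, 3 | shift missed |
| B, order known | 1 | 3 | 3 | 3, 3 | 1, 3 | shift missed |
| C, order known | 3 | 2 | 3 | 2, 3 | 3, 3 | false shift added |
| D, order unknown | 1 | 3 | 2 | 3, 2 | 1, 3 | shift missed |
| E, order unknown | 3 | 2 | 3 | 3, 3 | 3, 3 | no change |
| F, scheduled only | 1 | none | 3 | 1, 3 | 1, 3 | no change |

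Where the order is known, the rule takes the last value and the error can go either way (A and B against C). Where it is unknown, the tie rule takes the worst grade, so it can raise the baseline grade or leave it alone (D and E).

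**Step 4: size per patient.** With about 50 adults planned, one misclassified adult is 1/50 = 2 percentage points. The denominator in Section 6.6.3 is treated patients with at least one post-baseline value of that test, so the figure is slightly larger if fewer than 50 qualify. In the pediatric column, one patient is 1/6 = 16.7 points. For k misclassified adults the effect is at most 2k points: 0, 2 or 4 points for k = 0, 1 or 2. The documents give no basis for choosing k.

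**The case against.** The strongest reply is that the protocol already handles this. Day 1 laboratory samples are to be drawn before dosing, and no post-infusion safety sample is scheduled that day. The date wording is what lets the Day 1 pre-dose sample serve as baseline. This stands for all planned data and is why the point is small. It does not cover unscheduled or late samples, which the SAP rule neither excludes nor sends to the on-treatment period.

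Other objections also stand:

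- The optional 24-hour admission on Day 1 (Protocol Section 6.2.2.1) is for PK/PD sampling and creates no safety laboratory draw.
- The ECG rule in SAP Section 3.4 also selects by date. It names planned time points because ECGs are scheduled at 1, 2 and 4 hours on Day 1. The laboratory rule lacks that restriction, but the difference alone is not an error.
- Acute changes have other reporting routes. Liver-test thresholds are summarized over the on-treatment period (SAP Section 6.6.3.2). Under Protocol Section 8.2.2, abnormal results that need further tests or intervention are recorded as adverse events, and those dated on Day 1 count as on-treatment.

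A reader might infer that acute toxicity is systematically hidden and that the error always understates harm. The documents do not support this. The main rule takes the last value, not the worst, and Protocol Section 7.4 prompts repeats of values that are already abnormal. An improved repeat would lower the baseline grade and make a later Grade 3 look new, as in Case C.

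**Conclusion.** The concern holds in a limited form. SAP Section 3.4 states a rule that gives a wrong baseline when an off-schedule sample is drawn after the first infusion on Day 1, and the result conflicts with the on-treatment definition in Section 3.5. Patients with only scheduled, on-time samples are unaffected.

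Each misclassified adult moves the affected table by about 2 percentage points, assuming close to 50 evaluable adults. A patient counts as misclassified in the Grade 2 or lower to Grade 3 or higher table only if the displaced baseline, or the excluded value, changes which side of that boundary the patient falls on. The number of such patients cannot be derived from the documents, and a claim that many adults have wrong baselines would be a guess. The reach is confined to descriptive laboratory summaries; the primary QTcF analysis has its own baseline rule. The wording should still be corrected before database release, since the change is cheap and replaces a rule that is wrong when triggered.

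**What to change.** In SAP Section 3.4:

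1. Define the safety laboratory baseline as the last sample collected before the start of the first GO infusion, where the sample time is available.
2. If the time is missing, use the scheduled Cycle 1 Day 1 sample, or a single Day 1 sample presumed pre-dose under Protocol Table 1 footnote 11.
3. Apply the worst-grade tie rule only among samples known or presumed to be pre-dose.
4. In Section 6.6.3, count samples known to be post-infusion on Day 1 as on-treatment.
5. Flag any untimed unscheduled Day 1 sample in the listing and do not use it as baseline. Counting it as on-treatment would follow the same-day convention for adverse events in Section 3.5.1.

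The cost is a wording change and a revised baseline flag. Infusion time is collected (Section 3.5.1), but the documents do not say that laboratory sample time is. Section 5.2.5 treats laboratory results as log-page data, so the availability of times and visit labels should be checked against the CRF. The small downside is in item 5: an untimed extra sample may really be a pre-dose recheck, and counting it as on-treatment would then overstate toxicity. The flag keeps such cases visible.
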